2.4.5.4 Analyses of vital sign variables

The summary statistics (including number, mean, median, standard deviation, minimum, and maximum) of all vital signs variables (observed values and changes from baseline) will be provided for pre-infusion measurements and the change from pre-infusion to the completion of the infusion by visit and by patient and dose group. The vital signs measurements at each infusion rate change will not be summarized, but will be included in the patient listing.

The incidence of PCSAs at any time during the treatment-emergent adverse event period will be summarized by patient and dose group according to the following baseline status categories:

- Normal/missing
- Abnormal according to PCSA criteria

2.4.5.5 Analyses of electrocardiogram variables

The summary statistics (including number, mean, median, SD, minimum, and maximum) of all ECG variables (laboratory values, changes from baseline, and changes from rebaseline [LTS-switch group only]) will be calculated for each applicable visit or study assessment (baseline, each postbaseline time point) by patient and dose group. A listing of abnormal findings will be provided.

The incidence of PCSAs at any time during the treatment-emergent adverse event period will be summarized by patient and dose group or according to the following baseline status categories:

- Normal/missing
- Abnormal according to PCSA criterion or criteria

2.4.5.6 Analyses of Immunogenicity

ADA incidence and characterization

ADA status: ADA seroconversion is classified as always negative and ever positive. Baseline ADA status will be reported as negative or pre-existing ADA at initiation of treatment.

The following incidence rates will be summarized descriptively for each treatment group:

- ADA prevalence rate, defined as
$$100 \times (\text{number of patients with treatment-induced ADA} + \text{pre-existing ADA}) / (\text{number of evaluable patients})$$
- Treatment emergent ADA incidence, defined as
$$100 \times (\text{treatment boosted} + \text{treatment induced ADA positive patients}) / (\text{number of evaluable patients}),$$
- Treatment induced ADA incidence, defined as,
$$100 \times (\text{treatment induced ADA positive patients}) / (\text{number of evaluable patients with ADA negative at baseline}),$$
- Treatment boosted ADA incidence, defined as

100 x (treatment boosted ADA positive patients)/(number of evaluable patients with ADA positive at baseline).

Duration of ADA

The kinetics and duration of the immune responses will be analyzed as follow:

- Onset time of ADA will be analyzed descriptively using summary statistics minimum, Q1, median, Q3 and maximum.
- Duration of ADA will be analyzed descriptively using summary statistics minimum, Q1, median, Q3 and maximum. It will only be calculated for the patients with at least two ADA positive samples. The median duration and the quartiles will be reported.

ADA titers

- ADA peak titer, last titer, and geometric mean titer will be summarized.
- Graphs of ADA titer over time and boxplots of the highest post-baseline ADA titer will be provided.

ADA Response Classification

Response type classification will be provided.

- The number and percent of transient ADA response will be summarized descriptively. This will be performed for the patients with at least two post baseline samples where the last sampling timepoint is negative.
- The number and percent of persistent ADA response and its subclassifications will be summarized descriptively. This will be performed for the patients with treatment-induced ADA detected at two or more sampling time points post-baseline.
- The number and percent of indeterminate ADA response will be summarized descriptively. This will be performed for the patients with at least one post baseline sample.

Neutralizing ADA

- Incidence of neutralizing antibodies (inhibition of enzyme activity and inhibition of enzyme uptake) will be reported for both treatment naïve and switch patients
- Onset time of neutralizing ADA will be analyzed descriptively using summary statistics minimum, Q1, median, Q3 and maximum.
- Duration of neutralizing ADA will be analyzed descriptively using summary statistics minimum, Q1, median, Q3 and maximum. It will only be calculated for the patients with at least two ADA positive samples.

The following listings will be provided:

- Anti-avalglucosidase alfa alfa antibody titer values, neutralizing antibody, circulating immune complex, anti-avalglucosidase alfa IgE antibody, serum tryptase activity, complement activation, and skin testing performed
- Listings of anti-avalglucosidase alfa ADA and inhibitory antibodies
- Listings of anti-alglucosidase alfa ADA and inhibitory antibodies

Association of ADA with PK

The following analysis will be considered for switched patients: 1. Within Subject level AUC change from baseline to the last injection will be plotted by peak titer category. Gender will be separated by different color. 2. Between subject comparison of ADA-positive vs. ADA negative. Plot of AUC at baseline compared to timepoints where full PK assessment is available. Patients will be evaluated by titer categories based on titer category at the time of PK assessment. Patients will be separated based on treatment groups. 3. Summary table to include AUC and % change from Day 1 at each scheduled visit by peak titer categories. 4. Data will be assessed for switch patients as appropriate.

Association of ADA and PD marker

Hex-4 is a clinically relevant PD marker that is related to the drug's mechanism of action. Summary table of number (%) of patients with elevated urinary hex-4 by titer value at the specified visit (eg, peak titer categories) over time will be provided.

Evaluation of ADA on Relevant Safety Parameters

To evaluate the effect of ADA and NAb on AEs, the number and percentage of patients experiencing any TEAEs, any treatment-emergent SAEs, or any IARs, hypersensitivity (narrow SMQ), and Anaphylactic reaction (narrow SMQ) will be presented by the following sub-categories: 1. ADA status (ever positive, always negative) 2. ADA peak titer category (always negative, peak titer 100-800, 1600-6400, $\geq 12,800$) 3. ADA response type (always negative, transient response (if occur), and persistent responses subcategories: low response, intermediate response, high ADA response and tolerized at defined timepoints. 4. Correlation of frequency of IAR and ADA peak titer. 5. Neutralizing antibody status (always negative, ever positive).

Association of ADA with selected efficacy

Correlation analysis will be performed between immunogenicity (ADA titers, response categories and neutralizing ADA) and FVC, 6MWT, (raw and percent predicted), MIP, MEP.

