9.1.7 Immunogenicity

Immunogenicity assessments will include the following:

- Samples will be collected from patients and evaluated for anti-avalglucosidase alfa antibodies every month during the first 6 months and then every 3 months throughout the duration of the study. ADA seropositive patient serum will be assessed for neutralizing antibodies to avalglucosidase alfa which may include inhibition of enzyme activity and uptake.
- Samples will be collected from patients who were previously treated with alglucosidase alfa and evaluated for anti-alglucosidase alfa IgG antibodies every 6 months for up to the first 6 years of the study.
- Samples will be collected from patients and evaluated for IgE, complement activation, serum tryptase following moderate, severe, or recurrent mild IARs suggestive of hypersensitivity reactions ([Section 8.8.2](#)).
- In the event a patient exhibits signs or symptoms suggestive of systemic immune-mediated reactions involving skin and other organs while receiving alglucosidase alfa, serum samples are obtained for the evaluation of circulating immune complexes.
- Leftover antibody samples will be stored for further analysis as needed.
- See the study-specific laboratory manual as well as the Study Operations Manual (SOM) for guidelines on the collection and shipment of antibody and IAR samples and circulating immune complex samples.

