2.1.4.6 Anti-drug antibody and neutralizing antibody endpoints

Patients will be tested for anti-avalglucosidase alfa antibodies. Samples will be collected from patients for evaluation of ADA. ADA seropositive patient serum will be assessed for neutralizing antibodies to avalglucosidase alfa, including inhibition of enzyme activity and uptake.

The qualitative sample status of the ADA will be assessed and be categorized into the following classes:

- ADA-negative sample: a sample is considered negative if ADAs are not detected (ie, negative in screening assay or reactive in screening but negative in confirmatory assay).
- ADA-positive sample: sample in which ADA is detected, ie, sample generates an assay signal equal to or greater than the cut-point in the screening assay and is tested positive in the confirmatory assay.

The ADA titer of the positive samples will also be assessed. A titer represents a quasi-quantitative information on the level of ADA present in a sample. Confirmed positive samples are serially diluted until a negative result is achieved. The titer is subsequently defined as the reciprocal of the last dilution that tests positive. The minimal required dilution (MRD) will be incorporated in the final calculation.

The ADA attributes will be determined by the following conditions :

- Pre-existing ADAs: antibodies reactive with the study drug present in subjects before treatment.
- Treatment induced ADAs: ADAs developed de novo (seroconversion) following administration of the study drug. If the baseline ADA sample is missing or non-reportable and at least one reportable on-treatment ADA sample is available, the baseline sample will be considered as “negative”.
- Treatment boosted ADAs: Pre-existing ADAs that were boosted at least two titer steps from baseline (i.e., 4 fold increase in titers) following administration of the study drug (any time after the first drug administration).

The following kinetics of the ADAs will be analyzed:

- Onset of ADA is defined as the time period (in weeks) between the first study drug administration and the first instance of treatment induced ADAs.
- Duration of ADA will be calculated as the date of last treatment induced ADA sample minus date of first treatment induced ADA sample + 1.

The following ADA response classifications will be used:

1. Treatment-induced ADA- patients are ADA negative at baseline and have developed an ADA response

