 - a) Transient ADA response is defined as: 1) Treatment-induced ADA detected only at one sampling timepoint post-baseline (excluding the last sampling time point); or 2)

Treatment-induced ADA detected at two or more sampling time points post-baseline, where the first and the last ADA-positive samples (irrespective of any negative samples in between) are separated by a period of less than 16 weeks, and the subject's last sampling time point is ADA-negative

b) Persistent ADA response is defined as: 1) Treatment-induced ADA detected at two or more sampling time points post-baseline, where the first and the last ADA-positive on-treatment sample (irrespective of any negative samples in between) are separated by at least 16 weeks; or 2) Treatment-induced ADA detected in the last two sampling time points, irrespective of the time period in between.

The following subclassifications for persistent ADA response will be considered as well.

- Low response – if a patient peak titer ≤ 800 and positive at final assessment. This represents the first titer that is greater than a 4-fold increase from the assay minimum required dilution (MRD). Titers within this range would be considered as Low response.
- Intermediate response – if a patient was persistently seropositive but peak titer is 1600-6400 and is positive at final assessment.
- High response – if a patient was persistently seropositive and peak titer is ≥ 12800 and is positive at final assessment.

c) Tolerized – if a patient was persistently seropositive, but negative at the final assessment.
Time to tolerization is defined as (date of tolerization - date of initial seroconversion)/7
Tolerization date = date of the first negative values followed by all subsequent values negative.

d) Indeterminate ADA response – if the patient developed ADA at the last time point and all previous samples are ADA negative, therefore cannot determine whether the response will be transient or persistent in duration. Other timing that does not comply with transient or persistent definitions.

2. Treatment-boosted ADA – patients who have pre-existing ADA (positive at baseline) and have ADA titers boosted to a higher level by a greater than or equal to 4-fold increase (i.e., by greater than at least twice the 2-fold dilution level).
3. Treatment emergent ADA- combination of treatment induced and treatment boosted

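### ADA duration is summarised as if every response had ended: patients still positive at their last sample enter with a lower bound, which can only shorten the reported quartiles

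*SAP*

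**What the plan says.** SAP 2.1.4.6 gives the formula: "Duration of ADA will be calculated as the date of last treatment induced ADA sample minus date of first treatment induced ADA sample", plus one day. It names no event that ends a response and no indicator for a response that has not ended.

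SAP 2.4.5.6 gives the summary: "Duration of ADA will be analyzed descriptively using summary statistics minimum, Q1, median, Q3 and maximum". On who is included, it says "It will only be calculated for the patients with at least two ADA positive samples", whatever the result of the last sample. It then adds "The median duration and the quartiles will be reported".

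For neutralizing antibodies the same section says "Duration of neutralizing ADA will be analyzed descriptively using summary statistics minimum, Q1, median, Q3 and maximum", again in patients with at least two positive samples. It states no separate formula.

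The SAP expects some responses to be ongoing at the end. In 2.1.4.6 the intermediate and high persistent classes each carry the condition "and is positive at final assessment", and the low class has an equivalent one. The tolerized class is the counterpart: "if a patient was persistently seropositive, but negative at the final assessment".

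Protocol 9.1.7 sets the sampling: patients are "evaluated for anti-avalglucosidase alfa antibodies every month during the first 6 months and then every 3 months throughout the duration of the study".

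**The concern.** For a patient whose last sample is negative, last positive minus first positive describes a response that was seen to end. For a patient whose last sample is positive, the same subtraction gives the time from onset to the end of observation. The response lasted at least that long. The plan puts both kinds of value into one median with nothing to tell them apart.

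How long antibodies persist is a natural question for a multi-year extension, and immunogenicity is listed under the primary safety endpoint (Protocol 9.1). A censored value read as a completed duration makes persistence look shorter. It also makes groups with different follow-up look different when their responses may be alike.

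**Working it through.** The documents give no duration figure to reproduce, so the check covers the rule itself and then its possible size.

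**1. Is there a censoring rule anywhere?** No. SAP 2.1.4.6, 2.4.5.6 and 2.5.3 neither censor, flag nor separate patients who are positive at their last sample. The SAP does use Kaplan-Meier estimates for treatment-emergent adverse events (2.4.5.1) and for liver enzyme and bilirubin elevations (2.4.5.3).

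**2. Is follow-up unequal?** It can be. SAP section 2 pools the parent study with the extension. For anyone who did not roll over, the last parent-study ADA window in Appendix B Table 3 ends at day 198 (the footnote below the table gives day 273). The last extension window ends at day 2402, and 2402 / 365.25 = 6.6 years. Dropout adds to the spread. So does the additional follow-up phase, whose length depends on country (Protocol 6.2.1). The documents give neither the number of patients who did not roll over nor the dropout rate.

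**3. Direction.** Let D be the true duration and C the time from onset to the last sample. The plan records min(D, C), which never exceeds D, so censoring cannot lengthen any quartile.

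**4. Equal follow-up.** If C is the same for everyone, a quartile changes only when the true quartile lies beyond C. The upper quartile is affected once more than 25% are still positive at the end, and the median once more than 50% are. With exponential D of median 4 years and C = 6.5 years, the share still positive is 2^(-6.5/4) = 0.32. The median stays at 4.0 years, but the upper quartile prints as 6.5 years instead of 8.0.

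**5. Unequal follow-up.** Assumptions not in the documents: exponential D with median m, maximum follow-up 6.5 years, and 30% leaving at times uniform over 0 to 6.5 years. For t below 6.5, the proportion of recorded durations longer than t is

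S(t) = 2^(-t/m) × (1 - 0.3t/6.5).

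The plain median solves S(t) = 0.5:

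| True median m | Trial value t | S(t) | Plain median |
|---|---|---|---|
| 2 y | 1.76 | 0.543 × 0.919 = 0.499 | about 1.76 y |
| 4 y | 3.1 | 0.584 × 0.857 = 0.501 | about 3.1 y |
| 8 y | 5.0 | 0.648 × 0.769 = 0.499 | about 5.0 y |

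**6. On the plan's own sampling grid.** A simulation of 20,000 patients per scenario used the Appendix B Table 3 target days, the plan's formula and the two-positive rule. It assumed exponential onset (median 60 days) and exponential durations.

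| True median | Annual dropout | Plain median | Kaplan-Meier median, same spans |
|---|---|---|---|
| 0.5 y | 10% | 0.50 y | 0.51 y |
| 2 y | 10% | 1.50 y | 1.92 y |
| 4 y | 0% | 4.02 y | 4.02 y |
| 4 y | 5% | 3.08 y | 4.08 y |
| 4 y | 10% | 2.40 y | 4.08 y |
| 6.5 y | 0% | 5.83 y | not reached |
| 10 y | 0% | 6.09 y | not reached |

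In the last two rows the plan would print a definite median although more than half of the patients are still positive (53% and 66%).

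**7. A separate effect in the other direction.** Requiring two positive samples removes the shortest responses. With a true median of 0.15 years and no dropout, the plain median is 0.18 years with the rule and 0.08 without it. This selection is not censoring, and it matters only when responses are brief.

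**The case against.** The strongest reply is that ongoing positivity is already visible elsewhere. SAP 2.4.5.6 reports the persistent classes with their subclasses, last titer and titer-over-time graphs. A patient with two or more positives who leaves while positive cannot be classed as transient, because that class then requires a negative last sample. This stands: a reader of the whole immunogenicity section would not be told that such responses were brief. But none of those displays corrects the duration quartiles.

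Little depends on the figure, which also stands. Protocol 11.5.5 does not list duration. The analyses relating ADA to safety, pharmacokinetics, Hex4 and efficacy use status, titer, response class or neutralizing status. SAP 2.4.5 plans no systematic testing. Membership of the primary safety endpoint should not be used to inflate the point.

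The remedy is not fully at hand. The tolerization date is defined only for persistent responders, and no such event exists for neutralizing ADA. Starting the clock at the first positive while requiring a second one builds in some event-free time. SAP 2.4.7 itself refers to small patient numbers. These points raise the cost slightly but do not rescue the plain summary.

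A reader might infer that the reported medians will certainly be too short, or that the figure mostly measures length of follow-up. The documents support neither. The median is untouched when follow-up is equal and under half remain positive, and the second statement holds only if many patients remain positive, a share the documents do not give.

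**Conclusion.** Wrong as written. The stated rule treats lower bounds as completed durations, and this is a defect of the rule, not a missing detail. Censoring can only shorten the quartiles, by an unknown amount. For the median the effect is nil with equal follow-up and under half still positive; the upper quartile is affected once more than a quarter are. The median is shortened when follow-up is unequal or more than half remain positive.

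The figures of 3.1 for 4 years and 5.0 for 8 years illustrate the size under assumed exponential durations and uniform 30% dropout. They are not predictions for this trial. For neutralizing ADA the plan has the same kind of plain summary; that it uses the same subtraction is an inference, since no formula is given. The change is worth making but does not bear on any test.

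**What to change.** In SAP 2.1.4.6, define the end of response for every patient in the duration summary, transient as well as persistent, as the first negative sample with all later samples negative. This extends the existing tolerization-date rule. Define the corresponding event for neutralizing ADA. Censor patients who are positive at their last sample, at that sample.

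In SAP 2.4.5.6, report Kaplan-Meier median and quartiles with 95% confidence intervals, written as *not reached* where that applies, and the number of responses ongoing. State that the estimate is conditional on at least two positive samples. Moving the end from the last positive to the first lasting negative sample also lengthens durations by up to one sampling interval. In the simulation with a 4-year median and no dropout, the Kaplan-Meier median moved from 4.02 to 4.27 years, so the definition should be printed with the result.

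If the last-minus-first figure is kept, label it *observed span of positivity* and show the number still positive beside it.

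The cost is a few SAP definitions and some programming, with no new data. Confidence intervals will be wide in small groups, which reflects the information available.

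### SAP 2.4.5.6 gives the transient, persistent and indeterminate ADA percentages three different denominators, so they do not form one distribution and the persistent share is biased upward

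*SAP*

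**What the plan says.** SAP 2.4.5.6, under ADA response classification, asks for number and percent in each class and names the patients for each:

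- Transient: "This will be performed for the patients with at least two post baseline samples where the last sampling timepoint is negative".
- Persistent, with its subclasses: "This will be performed for the patients with treatment-induced ADA detected at two or more sampling time points post-baseline".
- Indeterminate: "This will be performed for the patients with at least one post baseline sample".

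The classes are defined in SAP 2.1.4.6.

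- Transient has two limbs. The first is "Treatment-induced ADA detected only at one sampling timepoint post-baseline (excluding the last sampling time point"), so the last sample is negative. The second is two or more positives spanning less than 16 weeks, with the condition that the "last sampling time point is ADA-negative".
- Persistent also has two limbs: two or more positives with first and last "separated by at least 16 weeks", or "Treatment-induced ADA detected in the last two sampling time points, irrespective of the time period in between".
- Tolerized applies "if a patient was persistently seropositive, but negative at the final assessment". Section 2.1.4.6 lists it as a separate item beside persistent. The paragraph of 2.4.5.6 on ADA and safety parameters lists it among the persistent subcategories. The response-classification bullets do not name it.

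Elsewhere in 2.4.5.6 the incidence rates have explicit denominators. Treatment-induced incidence, for example, is taken over evaluable patients who were ADA-negative at baseline.

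**The concern.** The transient and persistent subsets are each defined by a condition that the class itself requires: a negative last sample for transient, two or more positives for persistent. The indeterminate subset is not selected in this way. A reader who sees the three percentages in one table will take them as shares of the same patients, and they are not.

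Immunogenicity is part of the primary safety endpoint (protocol 9.1). The response classes are also reused in SAP 2.4.5.6 as subgroups for adverse events and infusion-associated reactions, and in correlations with efficacy. The natural question is what share of seroconverting patients develops a lasting response. The persistent percentage as written does not answer it, because seroconverters with a single positive sample are dropped from its denominator.

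**Working it through.** The plan states no figure on this point, so there is none to reproduce. The check applies the 2.1.4.6 definitions to the 2.4.5.6 subsets.

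**Notation.** AN = always negative; T1 = transient with one positive; T2 = transient with two or more positives; TOL = tolerized; P = persistent and positive at the last sample; I = indeterminate; N = all evaluable patients. TI = T1 + T2 + TOL + P + I is the number with treatment-induced ADA. All patients are assumed ADA-negative at baseline, with at least two post-baseline samples and complete follow-up.

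**Percentages as written.**

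- Transient = (T1 + T2) / (AN + T1 + T2 + TOL)
- Persistent = (P + TOL) / (P + TOL + T2)
- Indeterminate = I / N

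**On one denominator.** (T1 + T2)/TI, (P + TOL)/TI and I/TI sum to 100% when tolerized is counted within persistent.

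**Direction, persistent.** The written denominator omits T1 and I. The percentage is therefore never below the share of TI, and equals it only when T1 = I = 0.

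**Direction, transient.** The written denominator is part of N, so the percentage is at or above the share of evaluable patients. Compared with TI, it adds AN and drops P and I. It exceeds the share of TI only if AN < P + I.

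**Size.** The documents give no ADA frequencies, so the following mixes of 100 patients are assumptions chosen to show a range. Each cell gives the percentage as written, then the percentage of TI.

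| Mix | AN | T1 | T2 | TOL | P | I | Transient | Persistent | Indeterminate | Sum as written |
|---|---|---|---|---|---|---|---|---|---|---|
| A | 10 | 10 | 5 | 10 | 60 | 5 | 15/35 = 42.9; 15/90 = 16.7 | 70/75 = 93.3; 70/90 = 77.8 | 5.0; 5.6 | 141.2 |
| B | 30 | 10 | 5 | 10 | 40 | 5 | 15/55 = 27.3; 15/70 = 21.4 | 50/55 = 90.9; 50/70 = 71.4 | 5.0; 7.1 | 123.2 |
| C | 50 | 10 | 5 | 10 | 20 | 5 | 15/75 = 20.0; 15/50 = 30.0 | 30/35 = 85.7; 30/50 = 60.0 | 5.0; 10.0 | 110.7 |
| D | 70 | 10 | 5 | 5 | 8 | 2 | 15/90 = 16.7; 15/30 = 50.0 | 13/18 = 72.2; 13/30 = 43.3 | 2.0; 6.7 | 90.9 |
| E | 5 | 10 | 5 | 5 | 75 | 0 | 15/25 = 60.0; 15/95 = 15.8 | 80/85 = 94.1; 80/95 = 84.2 | 0.0; 0.0 | 154.1 |

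Of all evaluable patients, persistent is 13-80% across the mixes and transient is 15% in each. The transient percentage as written is above the share of TI in A, B and E, where AN < P + I, and below it in C and D.

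**Why two positives nearly decide the class.** SAP Appendix B Table 3 has 35 post-baseline antibody visits from Week 5 to Week 338. Two positives can be placed on them in 35 × 34 / 2 = 595 ways. Under 2.1.4.6, 537 (90.3%) are persistent or tolerized and 58 are transient. These are equally weighted visit patterns, not patients; they show the mechanism only.

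**When the effect vanishes.** In a simple simulation of seroconversion and loss on that schedule, scenarios in which nearly every seroconverter stayed positive gave about 100% persistent on either denominator. The gap opened when short responses were common: 74.3% as written against 61.9% of TI for persistent, 11.8% against 38.1% for transient, and a total of 86.1%.

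**The case against.** Four points can be made for the plan.

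1. The wording may set a minimum-data condition for classifying a patient rather than a denominator. This is possible but less natural. A negative last sample and two positive samples are results, not data requirements. On this reading, moreover, the SAP would state no denominator for these classes at all.

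2. The percentages can largely be recomputed. Counts are reported, treatment-induced incidence has a proper denominator, antibody listings are planned, and the adverse-event tables by response type show most classes side by side, though not indeterminate. This stands and limits the severity. It does not correct the percentages that will be printed.

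3. SAP 1.6 says some immunogenicity revisions were made for consistency with an integrated analysis plan, which is not among the documents. The same rule may apply across the programme. A reader might infer that the percentages cannot be compared with other studies; the documents do not show that. The fix should be checked against that plan.

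4. A negative last sample is necessary for transient response but far from sufficient, since always-negative and tolerized patients share it. This also stands. A reader might infer that the transient percentage is always inflated. It is not: relative to treatment-induced patients it is too low in mixes C and D, and the documents give no frequencies to say which case applies.

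**Conclusion.** The point holds. The three percentages rest on three different subsets, cannot be compared with each other, and need not sum to 100% (91-154% in the assumed mixes). The persistent percentage is biased upward relative to both seroconverters and evaluable patients: 72-94% as written, against 43-84% of treatment-induced patients. A reader might infer that it must approach 100% by construction. That is a tendency, not an identity, and many short multi-sample responses pull it down. The transient percentage is distorted: it is at or above the share of evaluable baseline-negative patients, but above the share of treatment-induced patients only when always-negative patients are fewer than those still persistently positive plus indeterminate.

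The sizes depend on the assumed mixes; the direction for persistent does not. The conclusion takes the quoted sentences as setting denominators and assumes baseline-negative patients with complete follow-up. With early drop-out, a few indeterminate patients can have two positives and stay in the persistent denominator. The consequence is moderate. This is a descriptive summary within the primary safety endpoint, SAP 2.4.5 plans no systematic testing of safety variables, and the counts are reported.

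**What to change.** In the response-classification block of SAP 2.4.5.6:

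- Use one denominator for transient, persistent (with its subclasses) and indeterminate: patients in the ADA evaluable set (SAP 2.3.4) with treatment-induced ADA.
- Show alongside the percentage of ADA-evaluable patients who were ADA-negative at baseline, the denominator already used for treatment-induced incidence.
- State in 2.1.4.6 and 2.4.5.6 that tolerized is a subcategory of persistent, as the safety-parameter paragraph already treats it, so that transient, persistent and indeterminate sum to 100%.
- Keep the conditions on number of samples and last result only as rules for assigning a class.

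The cost is SAP wording and a table footnote, plus a check against the integrated immunogenicity plan. No additional data are needed.
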